therapeutics such as discussed above, the addition of immunomodulators to the treatment regimen appear to be an excellent choice for agents which can reduce the pathogenicity of this disease by reducing the dysregulation of autoimmunity which is destructive of normal tissue and when unchecked rapidly leads to mortality. The use of naltrexone will be done in a randomized, double blinded manner whereas the use of ketamine will be unblinded and given as a rescue agent should a patient progress. Additionally should a patient be ineligible for the randomized portion of the study due to already being in stage 2B or stage 3 of the disease, they will be given the opportunity to enter the trial to receive ketamine without being randomized to naltrexone vs placebo.

3. Approach

Specific Aims

Aim 1: Determine whether treatment with low dose naltrexone, 4.5 mg by mouth daily, reduces progression of patients with COVID-19 from stage 1 or stage 2A to stage 2B or stage 3.

- 1.1: Determine the percentage of patients on naltrexone who proceed to requiring advanced oxygenation (hiflo nasal canula, non-rebreather, CPAP, BIPAP, or intubation)**
- 1.2: Determine the impact of naltrexone on development of renal failure, liver failure, cytokine storm, and ARDS.**
- 1.3: Determine the impact of naltrexone on mortality, length of stay, admission to ICU, length of stay in ICU, intubation, length of intubation, and time till recovery.**

Aim 2: Determine if ketamine can improve mortality in patients who progress the need for advanced oxygenation.

- 2.1: Determine the impact of ketamine on development of renal failure, liver failure, cytokine storm, and ARDS.**
- 2.2: Determine the impact of ketamine on mortality, length of stay, admission to ICU, length of stay in ICU, intubation, length of intubation, and time till recovery.**

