Patients who consent will be randomized to one of 2 arms: Arm 1 – low dose naltrexone 4.5 mg by mouth per day (can be given via NG tube if needed). Arm 2 – placebo by mouth per day. Treatment will be for 30 days past discharge. If the patient develops severe insomnia or shows symptoms of opioid withdrawal the dose of naltrexone can be decreased to 3 mg by mouth per day. If the patient continues to demonstrate issues on the 3 mg reduced dose of naltrexone the dose can be further reduced to 1.5 mg by mouth per day or held temporarily if needed. Reasons it may need to be held include if it is interfering with sedation, due to the unique issues with sedation in COVID-19 often requiring large amounts of opioids. Even low dose naltrexone seems to interfere with sedation in some of the patients. Since opioids, particularly fentanyl, are stored in fat, a patient who is starting on study who has been on opioid based sedation for 3 days or more can be started on a reduced dose of naltrexone (as above) or the naltrexone can be held from start and only ketamine used until their sedation is weaned to levels where clinically it is felt the naltrexone will no longer cause issues with sedation or signs of withdrawal. A patient should have naltrexone started by the time ketamine is no longer needed.

Imaging data, flowsheets, and medical notes will be abstracted to generate a daily summary of the patient's status to determine renal failure, liver failure, cytokine storm, ARDS, improvement vs progression of disease, need for advanced oxygenation, ICU status, and mortality.

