If at any point a patient requires advanced oxygenation (hiflo nasal cannula, non-rebreather, CPAP, BIPAP, or intubation) for more than 15 minutes they will then be given ketamine as a rescue treatment and remain on the Naltrexone or placebo. Ketamine will initially be given at a dose of 0.15 mg/kg based on total body weight (max 20 mg) every 6 hours (+/- 1 hour) by intravenous piggyback over 30 minutes. Ketamine will continue until the patient is deemed stable for low level oxygen. If the patient relapses after the ketamine is stopped they can be restarted on the ketamine. If the patient continues to worsen or displays evidence of cytokine storm (elevated markers of inflammation, evidence of ARDS, continuous fever) the dose of ketamine will be increased to 0.3 mg/kg IV every 6 hours (max 30 mg). The dose of ketamine can be reduced back to 0.15 mg/kg at the clinical decision of the physician investigators. If a patient has issues with hypertensive emergency the dose of ketamine can be held until the hypertensive emergency is controlled.

In addition, a patient can receive ketamine if they are not yet on advanced oxygenation if the investigating physician feels they are moving toward cytokine storm based on the markers of inflammation and clinical factors such as worsening imaging and unrelenting fever. If a patient transitions to comfort care the patient will remain in the study for data collection purposes. Study medications may be held if requested by the clinical team, patient, LAR or family.

Patients who at screening are already requiring advanced oxygen can be consented and enrolled in the study and immediately will skip the randomization and be placed on naltrexone and receive ketamine as the starting treatment in an open label manner.

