Sample Size Determination: We assumed that 20% of patients admitted to the hospital will show progression to requiring more oxygen, and that we want to detect if naltrexone reduces the progression rate to no more than 10%. With these assumptions, a sample size of 154 per arm (308 total) is required to have 80% power based on a two-sample t-test, using PASS 16.

Secondary Outcomes: To examine the potential impact of ketamine on mortality, we will use the chi-squared test to evaluate the hypothesis that mortality is reduced in the naltrexone arm. We will also estimate the difference in proportions using the Bayesian approach noted above. We will use a type 1 error rate of 0.05 for this secondary outcome.

For all remaining secondary outcomes, we will estimate the difference between the two arms and not test for differences between the two arms since these data will be used in planning future studies. For dichotomous outcomes (renal failure, liver failure, cytokine storm, and ARDS), we will use the Bayesian approach discussed for estimating the difference in proportions. We will use generalized linear models to estimate the difference in durations (number of days in ICU, number of days on a ventilator, and length of stay), evaluating the distribution to use based on the data. We will consider using the Poisson, negative-binomial, and normal distributions. We will use a Bayesian approach, using a flat prior on the difference in means parameter. We will calculate 99% credibility intervals for all of these secondary outcomes given the multiple outcomes being examined.

For statistical analysis the biostatisticians and Data analytics teams at Beaumont ([name] and [name]) will pull patients who were not on SINK, had COVID-19 with as close to a direct match to patients with similar profiles who were treated on the SINK study. The match to the patients on SINK will aim to compare the outcomes of the two groups, to see if there is a difference in the outcomes. The evaluation is a chart analysis aimed at focusing on the outcomes of the study.

Safety Measures:

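### The mortality test introduced as examining ketamine (Aim 2) compares naltrexone with placebo, so its result cannot be attributed to ketamine in either direction

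*Combined protocol and SAP*

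**What the plan says.** The Specific Aims keep the two drugs apart. Aim 1.3 is to "Determine the impact of naltrexone on mortality, length of stay" and further outcomes. The other main aim concerns ketamine: "Aim 2: Determine if ketamine can improve mortality in patients who progress the need for advanced oxygenation".

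Section 3.1 (Research Design) randomises naltrexone against placebo and nothing else. Randomised patients who come to need advanced oxygenation get ketamine whichever arm they are in: "they will then be given ketamine as a rescue treatment and remain on the Naltrexone or placebo". Ketamine may also start earlier at the investigating physician's judgement. Patients already on advanced oxygen at screening "will skip the randomization and be placed on naltrexone and receive ketamine as the starting treatment in an open label manner".

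The Statistical Analysis section then introduces its one formally tested secondary outcome as a way to examine the "impact of ketamine on mortality, we will use the chi-squared test to evaluate the hypothesis that mortality is reduced in the naltrexone arm". The type 1 error rate is 0.05, with no sidedness given. The remaining secondary outcomes are estimated between the two randomised arms without testing. A matched chart comparison of trial patients with COVID-19 patients outside the trial follows, in a short paragraph that does not mention ketamine.

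**The concern.** The sentence names one drug in its purpose and another in its hypothesis. Aim 2 is one of two aims, and mortality is the only secondary outcome with a test. As labelled, a lower death rate in the naltrexone arm could be reported as a ketamine benefit when ketamine did nothing. Equal death rates could be reported as a ketamine failure when ketamine helped both arms alike. Section 4 makes a larger multi-centre trial depend on success here, so a misattributed result could carry the wrong drug forward or drop a useful one.

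**Working it through.** **1. The plan's own figure.** The only sample size is 154 per arm, for progression of 20% versus 10% with 80% power. With one-sided 0.05 and unpooled variance:

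n = (1.645 + 0.842)² × (0.20×0.80 + 0.10×0.90) / 0.10² ≈ 154.6, or 155 per arm.

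A pooled-variance formula gives 157 and a noncentral t calculation 156. The stated figure is reproduced closely, and it sizes the naltrexone contrast. The plan gives no figure for mortality or for ketamine.

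**2. Who could serve as a ketamine-free comparator?**

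| Group | Naltrexone | Ketamine |
|---|---|---|
| Randomised to naltrexone, progresses | yes | yes, by rule |
| Randomised to placebo, progresses | no | yes, by rule |
| Open-label, already on advanced oxygen | yes | yes, from the start |

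No row holds patients assigned to progress without ketamine. At the plan's rates, expected progressors are 0.20 × 154 = 30.8 on placebo and 0.10 × 154 = 15.4 on naltrexone, or 46.2 of 308. These are progressors, not an exact count of ketamine recipients, because ketamine can start earlier or be held. Splitting randomised patients by ketamine use would not help, since that use follows worsening disease.

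**3. Do the analysis sets supply the comparison?** The full analysis set contains randomised patients grouped by assignment, and the per-protocol set is drawn from it. The safety set carries no outcome data, and the intent-to-treat set is named but not defined. Open-label ketamine recipients are therefore in no defined set that has outcomes.

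**4. What the test responds to.** This step is an illustration, and the mismatch does not depend on it. Write arm mortality as p × f × r, where p is the progression rate, f the case fatality after progression without a ketamine effect, and r the ketamine mortality ratio. Assumptions from outside the documents: f from 10% to 50%, no deaths without progression, and a one-sided test. Rejection rates come from exact binomial enumeration of the pooled z test (the chi-squared test with direction) at 154 per arm, critical value 1.645; two-sided rates at 1.960 are in brackets.

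- *Naltrexone inert, ketamine equal in both arms.* The difference is 0.20×f×r − 0.20×f×r = 0 for every r. At f = 40% the test rejects 5.0% of the time if ketamine is useless (r = 1) and 6.3% if it prevents three quarters of deaths (r = 0.25).
- *Naltrexone halves progression, ketamine useless (r = 1):*

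| f | Placebo vs naltrexone mortality | Test positive |
|---|---|---|
| 10% | 2% vs 1% | 20% (10%) |
| 20% | 4% vs 2% | 29% (16%) |
| 30% | 6% vs 3% | 35% (24%) |
| 40% | 8% vs 4% | 44% (31%) |
| 50% | 10% vs 5% | 51% (38%) |

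- *Naltrexone leaves progression at 20%, ketamine halves deaths only when given with naltrexone.* The arms are 0.20×f versus 0.20×f×0.5, the same mortality as in the table, so the rejection rates are identical.
- *Naltrexone halves progression and ketamine works (r = 0.25).* If it works equally in both arms, the positive rate at f = 40% falls from 44% to 20%. If it works only with naltrexone, the rate rises to 95%. At f = 20% the corresponding figures are 29% falling to 10%, or rising to 77%.

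A better ketamine can thus raise the positive rate, lower it or leave it nearly unchanged.

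**The case against.** The strongest reply is that this is a one-word slip. The same sentence states the tested hypothesis openly, the test is valid for Aim 1.3, and harm arises only if someone later reports an arm difference as a ketamine effect. The slip is plausible, but the documents do not settle it. If it is a slip, Aim 2 is left with no specified mortality analysis; if not, the test does not address its stated question. A correction is needed on both readings.

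A second reply is that other provisions cover ketamine patients. The section promises descriptive statistics for all secondary outcomes without limiting them to randomised patients, and the chart comparison appears to take in everyone treated on the trial. Both are true, so open-label outcomes are not wholly unplanned. Neither provision names ketamine or corrects the label. The chart comparison is not limited to ketamine recipients, sets no index time and does not exclude controls given ketamine. Section 2.2 says ketamine is in use for opioid sparing, though not that COVID-19 patients outside the trial receive it, so contamination of controls is possible rather than shown.

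It is also fair that the illustration rests on outside assumptions and that its equal-rates result follows by construction. At 10% and 20% fatality only about 4.6 and 9.2 deaths are expected in total (46.2 × f), where the chi-squared approximation is weak. The enumerated rates are exact for the test as written, and the conclusion does not use them.

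**Conclusion.** The concern holds and must be fixed. The mortality test estimates naltrexone versus placebo under a shared ketamine rule, and no randomised comparison in the trial estimates a ketamine effect. This follows from the design alone. With an equal ketamine effect and inert naltrexone, the tested difference is exactly zero. The 20% to 51% chance of a positive result with a useless ketamine is conditional on the assumed fatality range, no deaths without progression, 154 per arm and a one-sided test (10% to 38% two-sided). The estimates for the remaining secondary outcomes share the limitation as far as Aims 2.1 and 2.2 are concerned. The primary analysis stands, and so does the mortality test once it is labelled as naltrexone versus placebo.

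**What to change.** 1. Reword the mortality test as naltrexone versus placebo, serving Aim 1.3, and state that no randomised comparison in this trial estimates the ketamine effect. State the sidedness of the test in the same edit.
2. Declare Aim 2 exploratory, reported with an interval and no confirmatory claim. A purely descriptive report would also cure the error. Name the set of ketamine recipients whose outcomes will be reported.
3. Only if the chart comparison is to serve Aim 2: restrict it to trial patients who received ketamine and to controls without ketamine who are alive and on comparable oxygen support at a matched time zero, the first ketamine dose. Without that time zero, restricting to recipients brings in survival bias. Report placebo-arm, naltrexone-arm and open-label recipients separately, and record actual naltrexone exposure, because section 3.1 allows that "the naltrexone can be held from start and only ketamine used until their sedation is weaned" and adds: "Study medications may be held if requested by the clinical team, patient, LAR or family".

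Items 1 and 2 are text changes that need no extra patients or procedures. Their price is that Aim 2 becomes exploratory, which fits the plan in section 4 to confirm results in a larger trial. Item 3 needs chart abstraction of timed oxygen-device and ketamine data. Its randomised groups would be small (about 31 and 15 expected progressors); the open-label group could reach 500 − 308 = 192 if recruitment is full and 308 are randomised.

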3.2 Statistical Analysis

Descriptive statistics will be provided for all variables collected including patient demographics, numbers progressing to requiring more oxygen, and all secondary outcomes. Categorical variables will be summarized as counts and percentages. All continuous variables will be summarized as means \pm the standard deviation where normal or median and 25th, 75th percentiles if not normal. The minimum and maximum will also be provided.

Analysis Sets: Data analysis will be performed on a full analysis set (FAS), a per protocol set (PPS), an intent-to-treat (ITT) set, and a safety analysis (SA) set.

The FAS will be used for the primary analysis. The FAS will consist of all randomized subjects who receive at least one naltrexone/placebo treatment. All analyses using the FAS will group participants according to randomized treatment in an intent-to-treat analysis.

The PPS will be used for a supportive analysis and will be defined as all subjects included in the FAS who do not have any significant protocol deviations. All analyses using the PPS will group subjects according to treatment the subject actually received.

The safety data set will include all subjects with all safety data but will lack any outcome data. This data set will be used for reporting to the internal safety committee.

Missing Data: We will evaluate the potential impact of any missing data on analyses before deciding how to include missing data. Missing data will not be replaced by substitutions or imputation as long as the percent missing for any of the variables is less than 5%. Should the percent missing increase above 5%, we will use multiple imputation to replace missing data and conduct any analyses outlined below.

Primary Outcome: Progression to requiring more oxygen will be the primary outcome, and we will compare the percent patients progressing between the two arms of this study. The primary hypothesis is that the percent progressing for those in the naltrexone arm will be less than the percent progressing in the placebo arm. We will use the Pearson chi-squared test this hypothesis using a one-sided type 1 error rate of 0.05. We will also estimate the difference in proportion progressing using a Bayesian approach with independent Jeffrey's priors for both groups and numerical integration to obtain the credibility interval for the difference in proportions.

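### Mortality is tested at a full 0.05, side unstated, beside the primary test with no order between them; this puts the chance of at least one false efficacy claim at about 7-10% (one-sided) or 6-7% (two-sided)

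*Combined protocol and SAP*

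**What the plan says.** All the relevant text is in section 3.2 Statistical Analysis.

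- **Primary Outcome.** The hypothesis is that "the percent progressing for those in the naltrexone arm will be less than the percent progressing in the placebo arm". It is tested with a Pearson chi-squared test at a "one-sided type 1 error rate of 0.05".
- **Secondary Outcomes, mortality.** The paragraph opens by naming the effect of ketamine on mortality as its purpose. It then says "we will use the chi-squared test to evaluate the hypothesis that mortality is reduced in the naltrexone arm", and adds "We will use a type 1 error rate of 0.05 for this secondary outcome". The hypothesis is directional, but the side of the test is not given.
- **Secondary Outcomes, the rest.** "For all remaining secondary outcomes, we will estimate the difference between the two arms and not test for differences between the two arms". For these, "We will calculate 99% credibility intervals for all of these secondary outcomes given the multiple outcomes being examined".

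The section gives no testing order, gatekeeping rule, division of alpha or exploratory label for the mortality test. It also makes no statement about an overall error rate.

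**The concern.** The plan contains exactly two formal tests between the randomised arms, and each receives a full 0.05. The plan recognises multiplicity for the remaining secondary outcomes and handles it by estimating without testing. By that contrast, mortality is meant to be more than exploratory, yet it is the one secondary outcome left without protection.

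At stake is how a mixed result would be read. As written, nothing prevents a trial that misses its primary endpoint from reporting a mortality benefit as significant at 0.05. A mortality claim would probably carry more weight than the progression result, and the plan does not say what evidential status it would have.

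**Working it through.** **Inputs from the documents**
- Primary test: uncorrected Pearson chi-squared, one-sided 0.05.
- Mortality test: chi-squared, 0.05, side not stated, so both readings are carried.
- Progression 20%: "We assumed that 20% of patients admitted to the hospital will show progression to requiring more oxygen". Target on naltrexone 10%; 154 per arm; 80% power.
- Maximum recruitment 500 (section 3.1), used as 250 per arm.

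**Assumptions**
- Trial mortality is not given. A range of 1.5% to 15% is used. Section 1.1 quotes general figures of about 1.5% (United States), 3.6% (China) and 9.3% (Italy), which are not rates for this inpatient population.
- Deaths occur only among progressors (nested). Independence of the two outcomes is shown as the other extreme.

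**Step 1. Reproduce the plan's own figure.** The unpooled two-proportion formula, one-sided 0.05, gives

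n = (1.645 + 0.842)² × (0.2×0.8 + 0.1×0.9) / 0.1² ≈ 154.6 per arm.

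This agrees with the stated 154, so the sample size rests on a one-sided 0.05 test (two-sided variants without continuity correction need 196 to 201). Power at 154 per arm with a pooled-variance calculation is 79.4%.

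**Step 2. Nominal bounds for two tests.**
- Mortality one-sided: at most 0.05 + 0.05 = 10%. If independent, 1 − 0.95² = 9.75%.
- Mortality two-sided, counting only the benefit tail: at most 0.05 + 0.025 = 7.5%. If independent, 1 − 0.95×0.975 = 7.4%.

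**Step 3. Allow for correlation.** With progression rate p and mortality d nested within it, the correlation of the two test statistics is

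ρ = √[d(1 − p) / (p(1 − d))].

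For p = 0.20 and d = 0.036, ρ = √(0.0288 / 0.1928) = 0.386. The chance of at least one rejection under the null is 1 − Φ₂(z₁, z₂; ρ), where Φ₂ is the bivariate normal distribution function. z₁ = 1.645; z₂ = 1.645 (one-sided) or 1.960 (two-sided, benefit tail).

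**Step 4. Simulate the actual tests** under the null at 154 per arm, nested deaths. Repeat runs of 400,000 to 600,000 trials differ by about 0.1 percentage point. The size column is the one-sided mortality test alone, by exact enumeration.

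| Mortality | ρ | Size of mortality test | One-sided: nominal | One-sided: simulated | Two-sided, benefit: nominal | Two-sided, benefit: simulated |
|---|---|---|---|---|---|---|
| 1.5% | 0.247 | 6.1% | 9.4% | 10.5% | 7.2% | 6.9% |
| 2% | 0.286 | 6.3% | 9.3% | 10.6% | 7.1% | 7.0% |
| 3.6% | 0.386 | 5.3% | 9.1% | 9.4% | 7.0% | 6.9% |
| 5% | 0.459 | 5.0% | 8.9% | 8.9% | 6.8% | 6.8% |
| 9.3% | 0.640 | 5.0% | 8.3% | 8.4% | 6.4% | 6.5% |
| 15% | 0.840 | 5.0% | 7.3% | 7.3% | 5.8% | 5.8% |

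The simulated values above 10% occur where the mortality test alone exceeds its nominal 5%. They reflect small counts in the uncorrected Pearson test, not multiplicity. At 250 per arm with nested deaths, the one-sided range is 7.4% to 9.5% and the two-sided range 5.8% to 7.1%.

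**Step 5. How often would a false mortality claim stand alone?** In the nested one-sided simulation, a falsely significant mortality result comes with a non-significant primary in about 87%, 82% and 66% of cases at mortality 2%, 3.6% and 9.3%. These are the claims that a fixed order would block.

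**Step 6. Compare remedies.** If mortality is tested only after the primary rejects, the overall error cannot exceed that of the primary test, nominally 5%, and 154 per arm stands. An equal split (one-sided 0.025 each) also holds 5%, but it cuts primary power from 79.4% to 69.2% and needs 199 per arm for 80%.

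**The case against.** The strongest reply is that mortality is labelled secondary, only one secondary outcome is tested, and this is a single-center study whose results section 4 proposes to confirm in a larger multi-center trial. On that view, family-wise control over a primary and one secondary test is partly a matter of preference. That stands in part. The 5% stated under Primary Outcome is for the primary hypothesis alone, and that test keeps it. That mortality would be tested whatever the primary shows is also inferred from silence. But the plan reserves estimation without testing for the other secondary outcomes and gives mortality a formal test, so the label alone does not make that test exploratory.

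A reader might infer that the error rate is 8-11% where 5% was promised. The documents do not support this, for four reasons:
- They promise no overall rate.
- They do not say that the mortality test is one-sided. The directional wording and the one-sided primary make it plausible, but a two-sided test gives about 6-7%.
- Two tests of true size 5% cannot exceed 10% together. About 11% (11.05% in simulation) arises only near 2% mortality with mortality independent of progression. Independence is implausible here.
- Eight percent is too high as a lower end, because at 15% mortality with nested deaths the one-sided figure is about 7.3%.

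It can also be said that the mortality sentence names ketamine as its purpose, so which claims belong to one error family is unclear. That is fair, and it has to be settled together with the testing order.

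**Conclusion.** The concern holds in a limited form. Two formal tests between the same randomised arms each use a full 0.05, with no order between them and the side of the second unstated. The chance of at least one false efficacy claim is about 7-10% if mortality is one-sided and about 6-7% if it is two-sided and only benefit counts. These figures assume 20% progression, 154 per arm, deaths nested within progression, and mortality between 1.5% and 15%.

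It would go too far to say that the trial breaks a stated 5% guarantee or that its primary analysis is compromised. The excess matters only if mortality is claimed as confirmatory when the primary has failed, which the present text does not rule out. The change is worth making because it is small and specific; the primary analysis does not depend on it.

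**What to change.** In section 3.2 Statistical Analysis, under Secondary Outcomes:

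1. State whether the mortality test is one-sided or two-sided.
2. Reconcile the sentence's stated purpose (ketamine) with the comparison it makes (naltrexone versus placebo), so that it is clear which claim the test supports.
3. State that mortality will be tested at 0.05 for a formal claim only if the primary test rejects. Otherwise, report the difference in mortality with a 99% credibility interval, as for the other secondary outcomes, and make no significance claim.

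This takes a few sentences. The 154 per arm and the power of the primary test are unchanged. The small downside is that mortality cannot be formally claimed when the primary fails. Labelling the mortality test exploratory would also remove the ambiguity, but it gives up a formal mortality claim even when the primary succeeds.
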